3. EXPERIMENTAL PLAN

3.1 Study Design

The current study will be a phase 1b/2, multicenter, open label study conducted in 2 stages. Stage 1 will be an open-label, dose-escalation phase 1b study of RX-0201 administered in combination with everolimus. It is expected that 250 mg/m²/day or a lower dose of RX-0201 will be identified as safe and well-tolerated when administered in combination with everolimus. The initial dose of RX-0201 will be 125 mg/m²/day. RX-0201 will be administered by continuous intravenous infusion for 14 days followed by 1 week of rest. The dose of RX-0201 identified in Stage 1 will be studied further in the dose expansion portion (Stage 2). In Stage 1 and Stage 2, everolimus (10 mg) will be administered daily according to the approved label instructions.

Stage 2 will be an open-label, 2-arm phase 2 study of RX-0201 in combination with everolimus versus everolimus alone. Subjects will receive either RX-0201, at the dose identified in Stage 1, in combination with everolimus for up to 8 cycles until withdrawal of consent, pregnancy, substantial noncompliance with study procedures, intolerable adverse event, documented radiological disease progression (per RECIST ver. 1.1 see Appendix E), death, principal investigator judgment that it is in the best interest of the subject to stop treatment, or study discontinuation. For subjects receiving RX-0201 and everolimus therapy and, in the opinion of the investigator, is receiving benefit after 8 cycles, additional cycles of RX-0201 plus everolimus may be administered following discussions with the Sponsor. Prior to this amendment, subjects were randomized to receive everolimus alone. Subjects randomized to the everolimus only treatment arm will complete the study after 8 cycles but may continue to receive everolimus off-study.

The study endpoints are defined in Section 9.2.

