1.2 Secondary

- To assess the pharmacokinetics of RX-0201 in combination with everolimus (Stage 1)
- To evaluate parameters of clinical benefit as measured by duration of response, time to response, and response rate (Stage 2)
- To evaluate the safety and tolerability of RX-0201 in combination with everolimus versus everolimus alone (Stage 1 and Stage 2)

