3.4 Estimated Study Duration

3.4.1 Study Duration for Participants

Each subject should complete all study procedures in approximately 8 months (i.e., screening period up to 14 days; treatment period up to eight 21-day cycles, safety follow up approximately 30 days after the last dose of study medication).

Subjects in Stage 1 and Stage 2 may receive up to 8 cycles of RX-0201 until the earliest of disease progression (per RECIST ver. 1.1 see Appendix E), an intolerable RX-0201-related toxicity, withdrawal of consent, pregnancy, substantial noncompliance with study procedures, principal investigator judgment that it is in the best interest of the subject to stop treatment, or study discontinuation.

Subjects assigned to the RX-0201 and everolimus treatment arm, who the principal investigator feels are receiving benefit, may continue to receive treatment beyond 8 cycles following discussions with the Sponsor. The duration for these subjects will be >8 months with each additional cycle of treatment lasting 21 days.

The study duration is estimated at approximately 30 months.

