 - Tumor assessment, including CT/MRI as applicable. Subjects first meeting criteria for complete response or partial response at the last on-treatment tumor assessment should have a follow-up tumor assessment at the End of Trial or Early Termination visit providing it is ≥ 3 weeks from the last prior tumor assessment in order to confirm the response based on RECIST ver. 1.1 criteria.

Blood sample for biomarker analysis will be taken within 1 day of the tumor assessment.

Subjects also receiving RX-0201

- Turn off the RX-0201 infusion pump, disconnect the infusion bag and record the volume infused in the subject's medical record and eCRF if applicable.

7.9 Safety Follow-Up Visit – Stage 1 and Stage 2

Subjects will undergo the safety follow-up visit 30 days (+ 7 days) after the subject receives the last dose of everolimus or RX-0201, whichever is administered last.

The following procedures will be performed:

- Recording of concomitant medication(s), including any anticancer therapies administered subsequent to the administration of either protocol specified medication.
- Recording of adverse event(s). Serious adverse events will be reported immediately. Any adverse event that is considered related to study drug(s) will be followed to resolution or return to baseline.
- ECOG performance status
- Vital signs resting pulse, resting respiration rate, resting blood pressure (i.e., after the subject has been seated for at least 5 minutes) and temperature measurements.
- Other Assessment(s)

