9.5.2 Analysis of Key Study Endpoints

9.5.2.1 Adverse Events

Each reported adverse event will be assigned a System Organ Class (SOC), a higher level group term, a high level term and a preferred term according to the current version of the Medical Dictionary for Drug Regulatory Activities (MedDRA). The severity of adverse events will be assigned in accordance with the NCI CTCAE version 4.03 guidelines.

All adverse events will be listed by subject. The subject incidence rate of adverse events occurring between informed consent and first dose of study drug will be summarized by system organ class and preferred term for the Safety Analysis Set.

The incidence rate of treatment emergent adverse events, defined as all adverse events reported as new or worsened after the start of study drug, will be summarized by treatment group, system organ class, preferred term and maximum severity (where appropriate) for all adverse events, serious adverse events, adverse events leading to discontinuation of study specified treatment, adverse events leading to discontinuation from the study and fatal adverse events using subjects in the safety population. In addition, summaries of exposure adjusted adverse event rates may also be presented. These summary tables will also be repeated for treatment related adverse events. The number and percent of subjects reporting adverse events (all, serious, and related) will be tabulated by dose levels. Narratives of all serious and fatal adverse events will also be provided.

A listing and summary of the incidence of dose limiting toxicities present will be reviewed to make dose escalation decisions in Stage 1 review (dose limiting toxicity assessment set) will also be produced by treatment group and by subject.

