- 8 Everolimus (10 mg) will be taken at the clinic on Cycle 1 Day 1, and then at home every day thereafter
- 9 Subjects will bring all everolimus packaging (empty and full) to the clinic to determine drug compliance. For subjects receiving everolimus alone, compliance will be verified at least once per cycle when the subject returns to the site.
- 10 RX-0201 compliance will be checked at the Early Termination if the subject was receiving RX-0201 at the time of early termination.
- 11 All adverse events attributed to study drug(s) will be assessed until resolution or return to baseline
- 12 Disease assessment will occur at the end of every 2 cycles
- 13 Subjects first meeting criteria for complete response or partial response at the last on-treatment tumor assessment should have a follow-up tumor assessment at the End of treatment or Early Termination visit providing it is ≥ 3 weeks from the previous tumor assessment in order to confirm the response based on RECIST ver. 1.1 criteria
- 14 Biomarker blood samples will be collected within 1 day of the disease assessment (approximately at the end of every 2 cycles and at EOT/ET if applicable)
- 15 Tissue blocks or tissue sections from initial diagnosis or upon diagnosis of advanced metastatic disease will be available for submission to the central laboratory within approximately 4 weeks after initiation of study treatment; exceptions require written documentation of why a sample is not available and prior approval by the sponsor before randomization
- 16 Cycles 1-16 only
- 17 For subjects receiving RX-0201, one blood sample will be drawn prior to the end of infusion. If the sample draw is inadvertently missed, it can be drawn on Day 15 in a subsequent cycle.
- 18 For subjects receiving everolimus alone, the assessment may be completed by phone.

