- A diagnostic, medical or surgical procedure (e.g., surgery, endoscopy, tooth extraction, transfusion). However, the medical condition for which the procedure was performed should be reported if it meets the definition of an adverse event. For example, an acute appendicitis that begins during the adverse event reporting period should be reported as the adverse event and the resulting appendectomy should be recorded in the subject's medical records and eCRFs.
- A pre-existing disease or condition or laboratory abnormality present or detected before the initial screening visit and that does not worsen.
- An intervention not associated with an untoward medical occurrence (e.g., hospitalization for elective surgery or for social and/or convenience reasons).
- An overdose without clinical sequela.

Verbatim terms of AEs will be mapped to preferred terms and related system organ classes (SOC) using the Medical Dictionary for Regulatory Activities (MedDRA) Version 16.1. The incidence rate of treatment emergent adverse events (TEAEs), defined as all adverse events reported as new or

worsened after the start of study drug, will be summarized by treatment group, system organ class, preferred term and maximum severity for all adverse events, serious adverse events, adverse events leading to discontinuation of study specified treatment, adverse events leading to discontinuation from the study and fatal adverse events using subjects in the safety population. In addition, summaries of exposure adjusted adverse event rates may also be presented. These summary tables will also be repeated for treatment related adverse events.

Tables will summarize the number and percentage of subjects having an event in each system organ class and preferred term by dose group. The denominator used to calculate incidence percentages consists of subjects receiving at least one dose of RX-0201 in the combination of RX-0201 and Everolimus group.

Further tables will summarize the number and percentage of subjects having adverse events, classified according to severity and the number and percentage of subjects with related events. The order of SOCs presented in tables will be according to the internationally agreed order of SOCs according to MedDRA. Within each SOC, the preferred terms will be shown in alphabetic order.

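### Adverse events are tabulated as crude incidence although everolimus-alone subjects leave after 8 cycles and combination subjects may continue, which biases the expected incidence upward for the combination

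*Protocol*

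**What the plan says.** **Observation time.** For the everolimus-alone arm, Protocol 3.1 (repeated in SAP 5.1) states "Subjects randomized to the everolimus only treatment arm will complete the study after 8 cycles but may continue to receive everolimus off-study". Adverse event collection then runs to the safety visit 30 (+7) days after the last dose (Protocol 7.9). For combination subjects judged to be benefiting after 8 cycles, Protocol 3.1 states that "additional cycles of RX-0201 plus everolimus may be administered following discussions with the Sponsor", and Protocol 3.4.1 that they "may continue to receive treatment beyond 8 cycles following discussions with the Sponsor". No maximum is given. Protocol Appendix B limits some procedures to "Cycles 1-16 only", so treatment beyond 16 cycles is foreseen.

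**Objective.** A secondary objective in Protocol 1.2 reads "To evaluate the safety and tolerability of RX-0201 in combination with everolimus versus everolimus alone (Stage 1 and Stage 2"; SAP 4.1 repeats it.

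**Analysis.** Protocol 9.5.2.1 and SAP 8.10 count as treatment-emergent any event that is new or has worsened once study drug has begun, and set no end to the period. The incidence of such events "will be summarized by treatment group, system organ class, preferred term and maximum severity (where appropriate) for all adverse events", and likewise for serious and fatal events and those leading to discontinuation. On unequal time, SAP 8.10 offers only this: "In addition, summaries of exposure adjusted adverse event rates may also be presented". Protocol 9.5.2.1 says the same.

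**Who is tabulated.** The SAP is inconsistent. Section 7.2.3 puts everyone dosed with study drug in the safety set, by treatment received. The Safety Analyses text before 8.7 limits the final summaries to subjects with at least one dose of RX-0201. Section 8.10 limits the percentage denominator in the same way. The display groups in Section 7 name no everolimus-alone column.

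**The concern.** The percentage of subjects who ever had an event, and each subject's worst grade, can only rise with observation time. Here one group's time is capped by rule and the other's is not. If the two appear side by side, part of any excess in the combination column may reflect longer observation and not RX-0201, and the required tables give no means of telling the two apart. At stake is the trial's only safety comparison with everolimus alone. A reader can see that a group of 3 is small, but cannot see from the table that the two percentages cover different lengths of time.

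**Working it through.** The documents state no adverse event rate, so there is no plan figure to reproduce. The only sample-size figures (half-widths of ±0.28 and ±0.20 for 9-month PFS, Protocol 9.3) do not bear on this point.

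**Inputs from the documents**
- Control cap: 8 × 21 = 168 days = 168/30.44 = 5.52 months. With 30 days of follow-up, observation ends at Day 198.
- Median PFS: 4.5 months with everolimus alone, 9 months with the combination (Protocol 9.3).
- Analysis about 6 months after the last enrolled subject is treated (Protocol 9.1.2).
- Stage 2 size: 3 everolimus alone, up to 20 combination (Protocol 3.3).

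**Assumptions**
- PFS is exponential and stands in for time on treatment.
- Every combination subject without progression continues.
- The event hazard is constant and the same in both groups.
- Accrual is uniform over 12, 18 or 24 months (not stated in the plan).

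**Step 1: how many reach the cap.** The proportion still on treatment at 5.52 months is exp(−ln 2 × 5.52/median): 65.4% at a 9-month median and 42.7% at 4.5 months.

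**Step 2: effect of the unequal window.** Simulation of 400,000 subjects per scenario. The data cut-off is at 6 months plus a uniform accrual time. The event window is time on treatment plus 30 days, ending at the cut-off. The hazard is set to give the stated incidence when the window is capped at Day 198. Ranges run from 12 to 24 months of accrual.

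| | Median 9 months | Median 4.5 months |
|---|---|---|
| Share of combination event window after Day 198 | 33-45% | 23-30% |
| Uncapped incidence when common-window incidence is 20% | 27.6-31.3% | 24.4-25.8% |
| Uncapped incidence when common-window incidence is 30% | 39.6-43.7% | not tabulated |

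If the event rate after Day 168 falls to one quarter, the share of combination events after Day 198 falls to 12-18% (9-month median) or 8-10% (4.5 months).

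**Step 3: which events are affected, and what a cap leaves behind.** In closed form, let λ = ln 2/median, h = monthly hazard, T = cap and F = 30/30.44 = 0.99 months. Incidence is 1 − exp(−hF) × E, where E = λ/(λ+h) × (1 − exp(−(λ+h)T)) + exp(−(λ+h)T). With no cap, E = λ/(λ+h). The last column has no data cut-off and is an upper limit.

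| h per month | Everolimus, capped | Combination, capped at 8 cycles | Combination, treated to at most 12 months | Combination, no cap |
|---|---|---|---|---|
| 0.02 | 8.9% | 10.3% | 15.9% | 22.2% |
| 0.05 | 20.6% | 23.7% | 34.1% | 42.3% |
| 0.1 | 36.3% | 41.3% | 54.5% | 60.6% |
| 0.2 | 57.7% | 64.3% | 75.0% | 77.2% |
| 0.5 | 84.3% | 89.7% | 91.8% | 91.8% |
| 1.0 | 95.0% | 97.2% | 97.3% | 97.3% |

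The total gap at equal hazard is about 2 to 24 points. The missing cap accounts for up to 19.3 points of this (60.6 − 41.3 at h = 0.1) and only 0.1 at h = 1.0. The rest, 1.4 to 6.6 points, comes from the assumed longer PFS and remains after capping. Person-time rates remove it in expectation when the hazard is constant.

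**Step 4: chance.** With 3 controls the observed incidence can only be 0, 33, 67 or 100%; the exact 95% interval for 1/3 is 0.8% to 90.6%. Taking binomial counts of 3 and 20, the combination shows the higher percentage in 63-68% of trials when the true values are 20% against 28-31% (54% at 20% in both). At 30% against 40-44% it does so in 67-72% (52% at 30% in both).

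**The case against.** **The biased table may never be produced.** If the RX-0201-only rules in the SAP prevail, there is no everolimus-alone column. This stands, and it must be settled first. It does not remove the problem: if controls are tabulated, as the objective requires, the bias follows; if they are not, the objective goes unanswered.

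**The SAP makes some provision for time.** The Safety Analyses text calls for analyses by treatment cycle and week where appropriate. Adverse event tables by cycle would let a reader compare Cycles 1 to 8. This is a partial provision with no firm commitment, and neither it nor the optional exposure-adjusted rates must be produced.

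**The sizes lean high.** Stopping for toxicity, withdrawn consent or investigator judgment is ignored, and continuation is conditional on judged benefit, sponsor discussion and no progression. This is fair; the 4.5-month and reduced-rate scenarios show smaller effects.

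**Little depends on the comparison.** Safety methods are descriptive, the control arm has been closed, and no decision rule uses the contrast. This limits the importance. However, side-by-side percentages are read as comparisons even when no test is made.

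**A stronger reading is tempting:** that the combination will look more toxic simply because it is watched longer. The documents do not support it. Step 4 shows that with 3 controls the direction is far from assured, a real toxicity difference is possible, and continuation has no stated cap but is not unconditional.

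**Conclusion.** The concern holds as a bias in expectation. The observation window is unequal by rule, the required summary is crude incidence and worst grade without a common window, and the adjustment is optional. Under the stated assumptions, a 20% event in the common window becomes about 28-31% at a 9-month median PFS and 24-26% at 4.5 months, with no difference in hazard. Uncommon or late events are affected most; early, common ones hardly at all. Effects on maximum severity and serious events were not calculated; they should run in the same direction.

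The bias is smaller than the chance variation from about 3 controls, so nothing here predicts what the tables will show. It still merits correction before database lock, because it is systematic, invisible in the table and cheap to remove. Everolimus-alone subjects may also report Day 8 and Day 15 events by telephone (Protocol 7.5.4 and 7.5.5). That could add to the difference; it is not sized here and the change below would not remove it.

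**What to change.** In SAP 8.10 and 8.11, and in the Safety Analyses text before 8.7:

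1. Reconcile the RX-0201-only inclusion rule and denominator with the safety analysis set (SAP 7.2.3) and the secondary objective (SAP 4.1). State that everolimus-alone subjects are tabulated in their own column with their own denominator.
2. In every table that shows the two groups together, count events with onset from first dose to the earlier of 30 days after last dose or Day 198 (8 × 21 + 30). Use a fixed study day, not the end of Cycle 8, because Protocol 6.1.2 lets a cycle lengthen until recovery from adverse events. Put later combination events in a separate combination-only table so that none are lost.
3. Make exposure-adjusted rates by group mandatory. They also address the difference from unequal time on treatment that remains inside the common window.
4. State beside these tables that the control column rests on about 3 subjects, and give the exact interval.

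The cost is SAP wording and one onset-date filter, with no new data and no change to treatment or visits. The drawback is that the two adverse event tables must be read together for the full combination safety profile.

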3.2 Number of Centers

Up to 20 sites in the US will participate in this study. Sites that do not enroll subjects within 3 months of site initiation may be terminated.

3.3 Number of Subjects

In Stage 1 approximately 9 subjects will be enrolled to receive escalating doses of RX-0201 in combination with everolimus. The number of subjects enrolled into Stage 1 will vary depending upon the number of dose levels needed to determine the MTD up to a target dose of 250 mg/m²/day of RX-0201.

In Stage 2 approximately 23 subjects will be treated (i.e., 3 subjects in the everolimus arm and up to 20 subjects in the everolimus/RX-0201 arm).

3.4 Estimated Study Duration

3.4.1 Study Duration for Participants

Each subject should complete all study procedures in approximately 8 months (i.e., screening period up to 14 days; treatment period up to eight 21-day cycles, safety follow up approximately 30 days after the last dose of study medication).

Subjects in Stage 1 and Stage 2 may receive up to 8 cycles of RX-0201 until the earliest of disease progression (per RECIST ver. 1.1 see Appendix E), an intolerable RX-0201-related toxicity, withdrawal of consent, pregnancy, substantial noncompliance with study procedures, principal investigator judgment that it is in the best interest of the subject to stop treatment, or study discontinuation.

Subjects assigned to the RX-0201 and everolimus treatment arm, who the principal investigator feels are receiving benefit, may continue to receive treatment beyond 8 cycles following discussions with the Sponsor. The duration for these subjects will be >8 months with each additional cycle of treatment lasting 21 days.

The study duration is estimated at approximately 30 months.

3.4.2 End of Study

The end of the study is estimated to be approximately 30 days after the last subject completes the protocol specified treatment.

4. SUBJECT ELIGIBILITY

The following eligibility criteria are designed to select subjects for whom study participation is considered appropriate. All relevant medical and non-medical conditions should be taken into consideration when deciding whether this protocol is suitable for a particular subject. Eligibility

criteria may not be waived by the investigator, and conformance to the eligibility criteria is subject to review in the case of a Good Clinical Practice (GCP) or a regulatory authority audit. Any questions regarding a subject's eligibility should be discussed with the study sponsor and medical monitor prior to enrollment/randomization.

Before **any** study-specific procedures are performed, the appropriate written informed consent must be obtained (see Section 11.1).

4.1 Screening Log

Investigators will be expected to maintain a screening log of all potential study candidates that includes limited information about the potential candidate (i.e., age, sex, race), date, and outcome of the screening process (e.g., enrolled into study, reason for ineligibility, or declined to participate).

4.2 Inclusion Criteria

Disease related

- Documented histological or cytological diagnosis of renal cell cancer with a clear-cell component
- Measurable or evaluable disease defined by Response Evaluation Criteria for Solid Tumors (RECIST) ver. 1.1
- Must have received at least one course of therapy with a VEGFR-targeting tyrosine kinase inhibitor (eg, sorafenib, sunitinib, axitinib, pazopanib or tivozanib) and progressed within 6 months of planned first dose of study treatment.
- Prior therapy with cytokines (i.e., IL-2, Interferon) and/or VEGF-ligand inhibitors (i.e., bevacizumab) are permitted
- Prior vaccine therapy in the adjuvant setting is permitted
- Tissue blocks or tissue sections from initial diagnosis or upon diagnosis of advanced metastatic disease will be available for submission to the central laboratory within approximately 4 weeks after initiation of study treatment; exceptions (e.g., histology determined by fine needle aspirate or tissue is no longer available) require written documentation of why a sample is not available and prior approval by the sponsor before enrollment/ randomization
- ECOG performance status of 0, 1 or 2
- Life expectancy > 3 months

Demographic

- Males and females \geq 18 years of age at screening

Ethical

- Before any study-specific procedures are performed written informed consent must be obtained (see Section 11.1)

